12.11 Legal Aspects

The clinical study is submitted to the relevant national competent authorities in all participating countries to achieve a clinical trial authorization (CTA).

The study will commence (ie, initiation of study centers) when the CTA and favorable Ethics opinions have been received.

13 STUDY ADMINISTRATIVE INFORMATION

13.1 Protocol Amendments

Any amendments to the study protocol will be communicated to the Investigators by [REDACTED] or the Sponsor. All protocol amendments will undergo the same review and approval process as the original protocol. A protocol amendment may be implemented after it has been approved by the IRB/IEC, unless immediate implementation of the change is necessary for patient safety. In this case, the situation must be documented and reported to the IRB/IEC within 5 working days.

APPENDIX A: SCHEDULE OF PROCEDURES

Visit	Screening	Baseline	Week 2	Week 4	Week 8	Week 12/ Early Term	Week 16 (Follow-Up)
Study Day [Window (days)]	-14 to -1	1	14 [± 3]	28 [± 3]	56 [± 3]	84 [± 3]	112 [± 3]
Informed consent	X						
Demographics and medical history	X						
Eligibility assessment	X	X					
Diet and lifestyle counseling	X						
Randomization		X					
Vital signs	X	X	X	X	X	X	X
Weight	X	X	X	X	X	X	X
Height (and BMI calculation)	X		X	X	X		
ECG	X	X	X	X	X	X	X
Hematology	X	X	X	X	X	X	X
Physical examination [1]	X	X	X	X	X	X	X
Chemistry [2]	X	X	X	X	X	X	X
Pregnancy test (female patients only)	X	X [3]	X	X	X	X	X
Coagulation panel	X	X [4]				X	
Urinalysis	X	X				X	
Thyroid function test [5]	X[6]	X	X	X	X	X	X
Lipid panel, apolipoproteins, ApoCIII, lipoprotein(a)	X[7]	X	X	X	X	X	X
Lipoprotein particle analysis		X				X	X
LDL-C by ultracentrifugation		X				X	
	X	X	X	X	X	X	X
FSH, total and free testosterone [8], LH, CKMB, troponin I, reverse T3, ALP isoenzymes, P1NP, CTX, fibrinogen		X				X	X
HbA1c	X	X			X	X	

Footnotes on the next page.

APPENDIX A: SCHEDULE OF PROCEDURES (CONTINUED)

Visit	Screening	Baseline	Week 2	Week 4	Week 8	Week 12/ Early Term	Week 16 (Follow-Up)
Study Day [Window (days)]	-14 to 1	1	14 [± 3]	28 [± 3]	56 [± 3]	84 [± 3]	112 [± 3]
Hepatitis panel [9] and HIV	X						
Backup sample		X				X	
Genomic samples		X					
PK sampling [10]		X	X[11]	X	X	X	
Urine drug screen	X						
		X				X	
Fasting prior to visit [12] and Record time of statin dose		X	X	X	X	X	
Study drug dispensing and accountability by IRT[13]		X	X	X	X	X	
Review adverse events		X	X	X	X	X	X
Review concomitant medications	X	X	X	X	X	X	X

1. A complete physical examination will be performed at screening. Targeted, symptom-directed physical examinations will be performed at all other study visits.
 2. Includes calcium, phosphorus, GGT, CPK, and albumin. See Appendix B for a complete list of analytes.
 3. Urine test for human chorionic gonadotropin at randomization.
 4. Only PT and aPTT at baseline.
 5. Includes TBG, TSH, total T3 and T4, and free T3 and T4 except for Screening (see footnote 6).
 6. Exclude TBG.
 7. Exclude ApoCIII.
 8. Free testosterone will be calculated from total testosterone, [REDACTED], and serum albumin.
 9. Includes hepatitis B, HBsAg, HCV, and HCVAb
 10. Patients will be instructed not to take study drug prior to PK sampling except for Week 2 (see footnote 11).
 11. Patients will fast and arrive at the study site in the morning and following a predose PK blood draw, be administered study drug. All other assessments will be performed except for ECG. At 4 hours post dose, a second blood draw for PK will be taken. Following the blood draw, patients may discontinue fasting. Patients will then rest for 30 minutes, after which an ECG will be performed.
 12. Patients should fast for at least 10 hours prior to the visit.
 13. Treatments include MGL-3196 100 mg, MGL-3196 60 mg, or placebo. Each patient will receive study drug bottles labeled as A and B. Patients will take 1 capsule from bottle A and 1 capsule from bottle B once daily in the morning. No study drug will be dispensed at Week 12 or Early Termination. Study drug accountability will not be assessed at baseline.
 ALP = alkaline phosphatase; [REDACTED]; ApoCIII = apolipoprotein CIII; aPTT = activated partial thromboplastin time; BMI = body mass index; CKMB = creatine kinase MB; CPK = creatine phosphokinase; CTX = C-terminal telopeptide; ECG = electrocardiogram; FSH = follicle-stimulating hormone; GGT = gamma-glutamyl transferase; HbA1c = hemoglobin A1c; HBsAg = hepatitis B surface antigen; HCV = hepatitis C virus; HCVAb = hepatitis C virus antibody; HIV = human immunodeficiency virus; [REDACTED]; IRT = Interactive Response Technology; LDL-C = low-density lipoprotein cholesterol; LH = luteinizing hormone; P1NP = procollagen type 1 N-terminal propeptide; [REDACTED] PK = pharmacokinetic; PT = prothrombin time; [REDACTED]; T3 = triiodothyronine; T4 = thyroxine; Term = termination; TSH = thyroid stimulating hormone.

APPENDIX B: CLINICAL LABORATORY ANALYTES

Standard Chemistry Panel

Alanine aminotransferase	Albumin
Alkaline phosphatase	Amylase
Aspartate aminotransferase	Bicarbonate
Blood urea nitrogen	Calcium
Chloride	Creatine kinase
Creatinine	Direct bilirubin
Estimated glomerular filtration rate [1]	Gamma-glutamyl transferase
Glucose	Inorganic phosphorus
Lactate dehydrogenase	Lipase
Magnesium	Potassium
Sodium	Total bilirubin
Total protein	Uric acid

1. Calculated using Modification of Diet in Renal Disease (MDRD) formula.

Standard Hematology Panel

Hematocrit	Hemoglobin
Platelets	Red blood cell count
White blood cell count and differential	

Urinalysis

Bilirubin	Blood
Glucose	Ketones
Leukocyte esterase	Microscopy
Nitrite	pH
Protein	Specific gravity
Urobilinogen	

Coagulation

Activated partial thromboplastin time	Prothrombin time
International normalized ratio	

Serology

Hepatitis B	Hepatitis B surface antigen
Hepatitis C	Hepatitis C virus antibodies
Human Immunodeficiency Virus	Hepatitis C virus RNA (only if HCV Ab positive)

Lipid Panel

Total cholesterol	Triglycerides
High-density lipoprotein cholesterol	Non-high-density lipoprotein cholesterol
Calculated low-density lipoprotein cholesterol	Low-density lipoprotein cholesterol by preparative ultracentrifugation (Baseline and Week 12 only)

Additional Parameters

Apolipoprotein A1	Apolipoprotein B
Apolipoprotein CIII	Total and free thyroxine
Lipoprotein particle analysis	Total and free triiodothyronine
Sex hormone-binding globulin	Thyroid stimulating hormone
Follicle-stimulating hormone	Thyroid Binding Globulin
Luteinizing hormone	High-sensitivity C-reactive protein
Troponin I	Total testosterone
Alkaline phosphatase isoenzymes	Creatine kinase MB
Angiopoietin-like 3	Reverse triiodothyronine
C-terminal telopeptide	Proprotein convertase subtilisin/kexin type 9
Calculated free testosterone	Fibrinogen
Hemoglobin A1c	Procollagen type 1 N-terminal propeptide

Other assessments

Serum pregnancy test (female patients only)
Urine test for drugs of abuse
Pharmacokinetic sample
Backup samples
Genomic sample

APPENDIX C: SIMON BROOME REGISTER DIAGNOSTIC CRITERIA FOR HETEROZYGOUS FAMILIAL HYPERCHOLESTEROLEMIA

Definite familial hypercholesterolemia is defined as:

- Total-C >6.7 mmol/L (260 mg/dL) or LDL cholesterol above 4.0 mmol/L (155 mg/dL) in a child <16 years or Total-C >7.5 mmol/L (290 mg/dL) or LDL cholesterol above 4.9 mmol/L (190 mg/dL) in an adult. (Levels either pre-treatment or highest on treatment);

PLUS

- Tendon xanthomas in patient, or in 1st degree relative (parent, sibling, child), or in 2nd degree relative (grandparent, uncle, aunt);

OR

- DNA-based evidence of an LDL receptor mutation or familial defective apo B-100,

Possible familial hypercholesterolemia is defined as:

- Total-C >6.7 mmol/L (260 mg/dL) or LDL cholesterol above 4.0 mmol/L (155 mg/dL) in a child <16 years or Total-C >7.5 mmol/L (290 mg/dL) or LDL cholesterol above 4.9 mmol/L (190 mg/dL) in an adult. (Levels either pre-treatment or highest on treatment),

And at least one of the following:

- Family history of myocardial infarction below 50 years of age in 2nd degree relative or below 60 years of age in 1st degree relative; or
- Family history of raised cholesterol >7.5 mmol/L (290 mg/dL) in adult 1st or 2nd degree relative or >6.7 mmol/L (260 mg/dL) in child or sibling under 16 years of age.

Reference: DeMott K, Nherera L, Shaw EJ, et al. Clinical guidelines and evidence review for familial hypercholesterolemia: the identification and management of adults and children with familial hypercholesterolemia. London: National Collaborating Centre for Primary Care and Royal College of General Practitioners; 2008. Available at: <https://www.nice.org.uk/guidance/cg71/evidence/full-guideline-appendix-f-241917811>.

APPENDIX D: WHO CRITERIA (DUTCH LIPID NETWORK CLINICAL CRITERIA) FOR DIAGNOSIS OF HETEROZYGOUS FAMILIAL HYPERCHOLESTEROLEMIA

Diagnostic Scoring for Heterozygous Familial Hypercholesterolemia	
Family history	
First-degree relative with known premature (men <55 yrs, women <60 yrs) coronary and vascular disease,	1
OR	
First-degree relative with known LDL-C level above the 95th percentile	
First-degree relative with tendinous xanthomata and/or arcus cornealis,	2
OR	
Children aged less than 18 years with LDL-C level above the 95th percentile	
Clinical history	
Patient with premature (men <55 yrs, women <60 yrs) coronary artery disease	2
Patient with premature (men <55 yrs, women <60 yrs) cerebral or peripheral vascular disease	1
Physical examination	
Tendinous xanthomata	6
Arcus cornealis prior to age 45 years	4
Cholesterol levels	
LDL-C \geq 330 mg/dL (\geq 8.5 mmol/L)	8
LDL-C 250 – 329 mg/dL (6.5–8.4 mmol/L)	5
LDL-C 190 – 249 mg/dL (5.0–6.4 mmol/L)	3
LDL-C 155 – 189 mg/dL (4.0–4.9 mmol/L)	1
DNA analysis	
Functional mutation in the LDLR, apo B or [redacted] gene	8
Diagnosis (diagnosis is based on the total number of points obtained)	
Definite Familial Hypercholesterolemia	>8
Probable Familial Hypercholesterolemia	6-8
Possible Familial Hypercholesterolemia	3-5
Unlikely Familial Hypercholesterolemia	<3

Reference: Nordestgaard BG, Chapman MJ, Humphries SE, et al. Familial hypercholesterolemia is underdiagnosed and undertreated in the general population: guidance for clinicians to prevent coronary heart disease: consensus statement of the European Atherosclerosis Society. Eur Heart J. 2013;34(45):3478-3490a. Available at: <http://eurheartj.oxfordjournals.org/content/early/2013/08/15/eurheartj.eht273>.

1. INTRODUCTION

This document provides a description of the statistical methods and procedures to be implemented for the analyses of data from the study with protocol number MGL-3196-06. Any deviations from this Statistical Analysis Plan (SAP) will be documented in the final clinical study report.

2. STUDY OBJECTIVES AND STUDY DESIGN

2.1 Study Objectives

2.1.1 Primary Objective

The primary objective of this study is to determine the effect of each of two separate treatment groups (the “100 mg group” and the “60 mg group”) of once-daily oral dose of MGL-3196 and matching placebo on the percent change from baseline in low-density lipoprotein cholesterol (LDL-C) in patients with heterozygous familial hypercholesterolemia (HeFH).

2.1.2 Secondary Objectives

The secondary objectives of this study are the following:

- To evaluate the safety profile, including any changes in thyroid axis hormones, and tolerability of once-daily oral dosing regimen of MGL-3196 versus placebo after 12 weeks in patients with HeFH;
- To determine the effect of once-daily oral dosing regimen of MGL-3196 versus placebo for 12 weeks on the percent change from baseline on the following assessments in patients with HeFH:
 - Non-high-density lipoprotein cholesterol (non-HDL-C),
 - Apolipoprotein B (ApoB),
 - Total cholesterol (TC)/high-density lipoprotein cholesterol (HDL-C) ratio,
 - Triglycerides,
 - Lipoprotein(a),
 - ApoB/Apolipoprotein A1 (ApoA1) ratio, and
 - Lipoprotein particle assessment;
- To determine the effect of once-daily oral dose of MGL-3196 versus placebo for 12 weeks on the absolute change from baseline in LDL-C in patients with HeFH;
- To determine the effect of all patients (100 and 60 mg groups) on percent change from baseline in LDL-C; and
- To determine the effect of exposure to MGL-3196 on LDL-C lowering.

2.1.3 Exploratory Objectives

- [REDACTED]
- [REDACTED]
- [REDACTED]

- [REDACTED]
- [REDACTED]

2.2 Study Design

The population for this study is male and female patients ≥ 18 years of age who have met the diagnostic criteria for HeFH outlined by the Simon Broome Register Group (Protocol Appendix C) or World Health Organization (WHO)/Dutch Lipid Network (score >8 ; Protocol Appendix D).

This is a multi-center, double-blind, randomized, placebo-controlled study to evaluate the safety and efficacy of MGL-3196 in patients with HeFH. Patients who qualify for study inclusion will be randomized to receive one of two 12-week treatments: once daily oral dosing regimen of MGL-3196, or placebo (randomized 2:1) given orally once daily. Patients will self-administer MGL-3196 once daily each morning, and their statin medication each evening, during the 12-week treatment period.

To participate in the study, patients must be diagnosed with HeFH using standard accepted procedures and meet the study criteria. Patients must first provide written, informed consent and then undergo screening procedures within 14 days prior to randomization. Patients will begin taking their statin and other lipid lowering therapy at night at least 2 weeks before randomization, and will continue this practice for the duration of the study.

On the morning of Day 1, patients will be randomized in 2:1 fashion to receive either MGL-3196 100 mg or matching placebo. Following randomization, patients will undergo a 12-week treatment period and will periodically return to the study site (visits are planned at Weeks 2, 4, 8, 12 and 16) for assessment of drug exposure, safety laboratories, adverse events (AEs), vital signs (oral temperature, pulse rate, respiratory rate, and seated blood pressure).

The placebo group remains the placebo group throughout the study. At the Week 2 visit, in addition to other labs described below, a pharmacokinetic (PK) assessment will be made, that will include a pre-dose fasting MGL-3196 determination. Based on their randomization, patients will then be administered one dose of study drug (100 mg MGL-3196 or placebo) and a 4 hour postdose MGL-3196 PK assessment will be made while patients are fasting. A 12-lead electrocardiogram (ECG) will be obtained at 4 hours postdose after the 4 hour blood draw. Patients randomized to MGL-3196 100 mg will receive MGL-3196 60 mg between the Week 2 and 4 visits, while patients receiving placebo will continue to receive placebo. At the Week 4 visit, patients receiving MGL-3196 will either continue to receive 60 mg or be placed back on 100 mg depending on their Week 2 MGL-3196 level at 4 hours postdose. Patients with Week 2 postdose MGL-3196 blood levels $<1,500$ ng/mL will be placed on MGL-3196 100 mg, while patients with MGL-3196 blood levels $\geq 1,500$ ng/mL will continue to receive 60 mg.

Chemistry (including calcium and phosphorous) and hematology will be assessed at all study visits; a 12-lead ECG will be performed at all study visits; and coagulation and urinalysis will be performed at screening, baseline and end of study. At all study site visits, blood samples will be collected for the assessment of thyroid hormone parameters including thyroid stimulating hormone (TSH), total triiodothyronine (T3) and thyroxine (T4), and free T3 (FT3) and free T4 (FT4). Lipids (as described in the secondary objectives) will be assessed at all study visits except for low density lipoprotein (LDL) particle analyses, which will be assessed

at baseline, Week 12, and Week 16; LDL-C will be determined by ultracentrifugation at baseline and Week 12. Other biomarker assessments will include [REDACTED], assessed at all study visits. [REDACTED], Creatine kinase MB isoenzyme and troponin I, will be assessed at baseline and Weeks 2, 4, 8, 12 and 16. Follicle-stimulating hormone, total and free testosterone, luteinizing hormone, reverse T3, fibrinogen, alkaline phosphatase isoenzymes, procollagen type 1 N-terminal propeptide, and C-terminal telopeptide will be assessed at baseline, Week 12, and Week 16; free testosterone will be calculated from total testosterone, SHBG, and serum albumin. Patients will be evaluated for adverse events throughout the study.

Following the first dose of MGL-3196 and thereafter, the dose of MGL-3196 will be down-titrated if TSH is below the lower limit of normal (LLN) with a >50% change from baseline confirmed on 2 consecutive assessments. Down-titrations will be as follows: the 100 mg dose would be decreased to 80 mg, and an 80 mg dose would be decreased to 60 mg. Following down-titration, TSH testing will resume according to the schedule of procedures. A second down-titration is permitted (i.e. to 40 mg).

A Data Safety Monitoring Board (DSMB) will oversee the study to ensure patient safety and to advise if any dosing alterations are recommended. The DSMB will review safety data including thyroid hormone effects, liver-related events (ie, clinically meaningful elevations in liver enzymes alanine aminotransferase [ALT], aspartate aminotransferase [AST], and bilirubin), and other efficacy (lipid parameters) and safety data as needed. The DSMB will perform regularly scheduled reviews as well as an additional review if necessary.

The schedule of procedures can be found in Protocol Appendix A.

2.3 Study Endpoints

2.3.1 Efficacy Variables

The primary efficacy parameter is mean percent change from baseline in LDL-C.

The secondary efficacy parameters include the following:

- Mean percent change from baseline in non-HDL-C, ApoB, TC/HDL-C ratio, triglycerides, lipoprotein(a) (Lp(a)), ApoB/ApoA1 ratio, Apolipoprotein CIII (ApoCIII), and lipoprotein particle assessment;
- Absolute change from baseline in LDL-C;
- Mean percent change from baseline in LDL-C for all patients on study drug (60-100 mg); and
- Mean percent change from baseline in LDL-C according to MGL-3196 exposure.

The exploratory efficacy parameters include the following:

- [REDACTED]
- [REDACTED]
- [REDACTED]
- [REDACTED]

2.3.2 Pharmacokinetics

Blood samples for PK assessments will be obtained fasting pre-dose from patients at the Baseline Visit (Day 1), Weeks 2, 4, 8, and 12, and the Early Termination Visit. Blood samples for PK assessment will also be obtained 4 hours post-dose from patients at Week 2 under fasting conditions. Statin PK will also be assessed at baseline and Week 2 visits and may be assessed at later visits.

2.3.3 Safety Variables

Safety variables to be assessed include safety laboratory tests, vital signs, 12-lead ECG with rhythm strip, physical examinations, assessment of adverse events, and clinic assessments.

3. STATISTICAL METHODOLOGY

3.1 Baseline, Endpoint, and Other Statistical Considerations

Baseline for all efficacy and safety variables will be defined as Baseline visit (Day 1). If the measurement at this visit is missing, the last measurement prior to the first dose of randomized study drug will be used.

Only lipids measured less than 2 days after the last dose of study drug are considered as a valid post-baseline lipid assessment.

Post-baseline lipid assessments will be assigned a visit number based on the date of assessment relative to the first dose of the double-blind study drug. Visit windows will be defined as the scheduled time from dosing date with a 7-day window (± 7 days). Within a visit window, if a scheduled visit occurs, then the measurement from this scheduled visit will be used as the measurement for this visit window. If no scheduled visit occurs within a visit window, the last measurement within the window will be used. If no visits occur within a visit window, the measurement of this visit will be treated as missing.

Descriptive statistics (number of patients, mean, standard deviation, median, minimum, and maximum) will be used to summarize the continuous data. Discrete measures will be summarized using counts and percentages.

The summary and analysis of efficacy and safety data will be based on the MGL-3196 and placebo group. The primary efficacy and selected secondary endpoints will also be analyzed by MGL-3196 exposure level for the patients taking MGL-3196: higher exposure group and lower exposure group. The MGL-3196 exposure levels are determined by the plasma MGL-3196 concentration at Week 2 and later visits to represent the overall MGL-3196 exposure level for patients. That is, patients satisfies one of the following two conditions will be included in high exposure group: projected Week 2 AUC >5000 mg*h/L, or if Week 2 AUC <5000 but Week 4 predose >1.5 ng/mL (if on 60mg). Another analysis will be based on the [REDACTED] level for the patients taking MGL-3196: higher increase ($\geq 140\%$) and lower increase ($<140\%$) in [REDACTED] from baseline to Week 12.

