1.2 Rationale for Phase 2 HeFH Study Design

Doses of 80-200 mg per day of MGL-3196 appeared to have similar effects on lipids after 14 days of dosing in a modest number of otherwise-healthy volunteers with mildly elevated LDL-C; effects in patients with HeFH or in individuals dosed for longer periods may differ. Results of the completed clinical studies, including robust lipid changes observed in the MAD and MGL-3196-03, suggest that MGL-3196 is suitable for once-daily dosing, and that it can be dosed with or without food. Based on the dose-related lipid effects, the doses of MGL-3196 planned for the Phase 2 study in HeFH patients is 100 mg/day (range of projected mean exposure ~4000–9000 ng*hr/ml), to be given once-daily without regard to food.

Patients with HeFH typically take high dose statins, particularly atorvastatin and rosuvastatin with ezetimibe^{21,23} to achieve therapeutic targets. MGL-3196's mechanism of cholesterol lowering is complementary to statins.⁵ MGL-3196 provides additional benefits, potently lowering triglycerides and, like other thyroid agonists appears to reduce Lp(a), a particularly atherogenic particle frequently elevated in HeFH, including severe HeFH.

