MGL-3196-06 employs a simple adaptive design, that will optimize dose for individuals randomized to MGL-3196. Based on studies in 129 individuals safely dosed for up to two weeks with MGL-3196, at doses ranging from 50- 200 mg per day, MGL-3196 drug exposure shows variability in exposure between individuals and higher exposure in some individuals, particularly at the 200 mg dose, which will not be used in the Phase 2 HeFH study. This is similar to statins, which are also liver-directed drugs that interact with liver and gut uptake transporters. MGL-3196 exposures are less variable at the lower doses, including 60-100 mg, that will be studied in this Phase 2 study. There are no studies that suggest that exposure to MGL-3196 will be different in patients with HeFH or that HeFH patients have consistent alterations in drug metabolizing enzymes or transporters which may be involved in MGL-3196 uptake by the gut or liver. Unlike statins, there has been no myopathy associated with higher drug exposures of MGL-3196 in humans or animal studies; nonetheless, the design of the HeFH Phase 2 trial is adaptive in that

dose adjustments of MGL-3196 will be made after 2 weeks of dosing to optimize exposure for the individual patient.

MGL-3106 exposure variability, which may relate to polymorphisms in drug metabolizing enzymes and transporters, may occur in some (~25-30%) patients in the HeFH study who may have higher than the target exposure (4000-9000 ng^{*} hr/ml) to MGL-3196 at the 100 mg dose. A few patients (10%) (likely to be non-LDL responders) may have drug levels lower than the target exposure. Therefore, the trial design is adaptive to optimize both safety and efficacy. Randomization will be 2:1, 100 mg MGL-3196 to placebo. The drug level of MGL-3196 reaches steady state in a few days. At the Week 2 clinic visit, an assessment of MGL-3196 PK will be performed, including measurement of the pre-dose and T_{max} (4 h) levels of MGL-3196. These two assessments will allow an accurate assessment of MGL-3196's total exposure. Between weeks 2-4, pending results of the PK measurements, all patients randomized to drug will be treated with 60 mg of MGL-3196. Based on the C_{max} value of MGL-3196 at Week 2, an unblinded clinical pharmacologist will assign MGL-3196 dose to the time period, Weeks 4-12. At Week 4, patients who had a Week 2 $C_{max} \geq 1500$ ng/ml will continue on 60 mg of MGL-3196 and those with $C_{max} < 1500$ ng/ml will be placed back on 100 mg/day.

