1.2.3 Safety Monitoring

Careful safety monitoring will be performed including assessment of safety labs, vital signs, ECGs, drug levels to help assure patient safety during this Phase 2 study, particularly during the first few weeks when drug levels will be established. As discussed, a DSMB (including lipid, thyroid, liver and statistical experts) will oversee the study to ensure patient safety and to advise if any dosing alterations are recommended. The DSMB will review safety including thyroid hormone effects, liver-related events (ie, clinically meaningful elevations in liver enzymes ALT, AST, and bilirubin), muscle and cardiovascular effects, and other efficacy (lipid parameters) and safety data as needed. The DSMB will perform regularly scheduled reviews.

Biomarkers of thyroid action, [REDACTED] TSH, free T4 and free T3 levels will be assessed at study visits. TSH levels will be monitored in the Phase 2 studies as described in the protocol, and downward dose adjustments will be made in any patients who show significant reduction of TSH on two occasions of at least 50% and below the normal range. However, such a reduction in TSH is extremely unlikely. The target exposures at the clinical doses to be used in the Phase 2 studies

are in the range of 4-9000 ng*hr/ml, at least 10 fold lower than exposures where modest, reversible TSH suppression might be anticipated (IB). Small decreases in TSH within the normal range might be observed in HeFH patients treated with MGL-3196 because we anticipate that hepatic T3 production may increase with MGL-3196 treatment, and T3 (the active thyroid hormone) is the key regulator of TSH.

Small decreases in prohormone FT4 of 20% but remaining within the reference range such as observed in MGL-3196 Phase 1 studies are not considered to be clinically meaningful. Most recent human data suggest that maintaining a normal level of active hormone FT3 may be sufficient to establish euthyroidism.²⁷ In the Phase 1 MAD study, a single subject on the 200 mg dose with the highest drug exposure in the study had a FT4 below the standard reference range (0.7 ng/dL), and in MGL-3196-03, a few subjects had levels of 0.7 ng/dL; in MGL-3196-04, a few subjects, 0.9 ng/dL. After two weeks of dosing in the MAD study, most FT4 levels appeared to reach steady state. Per thyroid expert advice, given the short duration of the HeFH study (12 weeks), and normal TSH and FT3, dose adjustments will not be made to maintain FT4 levels above 0.7 ng/dL.

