5 STUDY TREATMENTS

5.1 Treatment Groups

Patients who qualify for study inclusion will initially be randomized (2:1) to receive once-daily MGL-3196 100 mg or once-daily matching placebo given orally in the morning. All patients randomized to MGL-3196 will initially receive 100 mg QD through the week 2 visit, then 60 mg QD until the week 4 visit. At the week 4 visit, patients receiving MGL-3196 will be placed back on 100 mg if their week 2 MGL-3196 level 4 h postdose is < 1,500 ng/mL and described as the “100 mg group”; if the level of MGL-3196 \geq 1500 ng/ml they will continue to receive 60 mg QD for weeks 4-12 and will be described as the “60 mg group”. In summary, the assigned treatment groups are as follows:

- Placebo
- “100 mg group”: patients administered MGL-3196 100 mg for weeks 1-2, 60mg between week 2-4 visits, and 100 mg for weeks 4-12
- “60 mg group”: patients administered MGL-3196 100 mg for weeks 1-2 and 60 mg for weeks 2-12

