3.7.3 Subgroup Analysis of LDL-C

The subgroup analysis of LDL-C will be based on the mITT population. Since the analyses are for descriptive purposes only, no adjustments will be made for multiplicity.

The analysis of LDL-C will be performed based on MGL-3196 exposure group. In the analysis of LDL-C based on MGL-3196 exposure group, the patients who are taking MGL-3196 will be categorized into higher and lower exposure groups. The same ANOVA and ANCOVA models will be used, with pairwise comparisons between each exposure group versus placebo will be provided.

The analysis of LDL-C will also be performed based on SHBG group. In the analysis of LDL-C based on SHBG group, the patients who are taking MGL-3196 will be categorized into groups with higher increase or lower increase of SHBG from baseline to Week 12. Patients who are taking MGL-3196 but do not have Week 12 SHBG values will not be included. The same ANOVA and ANCOVA models will be used, with pairwise comparisons between each exposure group versus placebo to be provided.

The final dose of MGL-3196 (100 mg or 60 mg) will also be used to repeat the primary efficacy analysis. Similar to the exposure group, an analysis will be performed, but with the final dose of MGL-3196 to categorize patients who are taking MGL-3196.

The primary efficacy analysis of LDL-C will be repeated based on the following subgroups:

- Statin subgroup (80 mg Atorvastatin, 20/40 mg Rosuvastatin, or No/Low Dose Statin);
- Exposure group, SHBG group, in combination with statin subgroup;
- Gender subgroup (male, or female);
- Exposure group, SHBG group, in combination with gender subgroup;
- Baseline LDL-C value (<100 mg/dL, or \geq 100 mg/dL);
- Statin and baseline LDL-C subgroup;

- Exposure group, SHBG group, Final MGL-3196 dose group, in combination with baseline LDL-C subgroup;
- Baseline BMI value (<25 kg/m², or ≥25 kg/m²; and <30 kg/m², or ≥30 kg/m²);
- Exposure group, SHBG group, Final MGL-3196 dose group, in combination with baseline BMI subgroup;
- Average TSH between baseline and screening subgroup (<2 mIU/L, or ≥2 mIU/L);
- Exposure group, SHBG group, Final MGL-3196 dose group, in combination with average TSH between baseline and screening subgroup;

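### The SAP's high-exposure AUC cut-off, as printed in mg·h/L, is 556 to 1,250 times the protocol's exposure range, so taken literally its AUC condition selects nobody

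*SAP*

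**What the plan says.** SAP 3.1 is the only place in either document that defines the exposure groups. A patient is in the high-exposure group if one of two conditions is met: "projected Week 2 AUC >5000 mg*h/L, or if Week 2 AUC <5000 but Week 4 predose >1.5 ng/mL (if on 60mg". The first AUC figure carries the unit mg·h/L. The second, in the predose condition, carries no unit.

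The protocol states MGL-3196 exposure only in ng·h/mL:

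- Section 1.2, for 100 mg/day: "range of projected mean exposure ~4000–9000 ng*hr/ml".
- Section 1.2.2, on the roughly 25-30% of patients expected above target at 100 mg: "who may have higher than the target exposure (4000-9000", in the same unit. It also expects about 10% of patients below target.
- Section 1.2.3, on target exposures: "are in the range of 4-9000 ng*hr/ml", evidently shorthand for the same range.

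The groups are then used in several analyses. SAP 2.3.1 lists as a secondary parameter "Mean percent change from baseline in LDL-C according to MGL-3196 exposure". SAP 3.7.3 says "the patients who are taking MGL-3196 will be categorized into higher and lower exposure groups", compares each group with placebo, and crosses exposure with statin, gender, baseline LDL-C, BMI and TSH subgroups. SAP 3.7.5 applies the grouping to the secondary and exploratory endpoints, and SAP 3.8.2.1 to liver enzymes.

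**The concern.** The two documents describe the same quantity on scales three orders of magnitude apart, and neither explains the change of unit. If the printed cut-off is used, every patient falls below it. The rule then stops being a split on AUC and becomes a split on one predose concentration at Week 4. All the analyses listed above would carry a label, high versus low exposure, that no longer means what the AUC threshold was meant to express.

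Timing also matters. If the error is noticed only after LDL-C results are visible, the corrected cut-off would be chosen with knowledge of the outcome it is meant to explain.

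The predose condition, which would then carry the whole definition, has two loose ends of its own:

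- **Dose qualifier.** It does not say whether being on 60 mg refers to the dose when the Week 4 predose sample is taken or to the dose from Week 4 onward. The first is the more natural reading. It would cover every active patient following the schedule: Protocol 5.1 has 100 mg first, "then 60 mg QD until the week 4 visit", and SAP 2.2 agrees: "Patients randomized to MGL-3196 100 mg will receive MGL-3196 60 mg between the Week 2 and 4 visits".
- **Sample.** The Week 4 predose sample is listed in Protocol 6.4.3, Protocol 8, Appendix A and SAP 2.3.2. It is missing from the PK lists in the protocol synopsis and SAP 3.9.

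**Working it through.** The cut-off is a chosen threshold, so there is no derivation in the plan to reproduce. The check is a unit conversion followed by tests of scale.

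**Inputs.** Cut-off 5000 mg·h/L (SAP 3.1). Exposure range 4,000-9,000 ng·h/mL (Protocol 1.2, 1.2.2). Week 2 four-hour concentration threshold 1,500 ng/mL (Protocol 5.1, SAP 2.2). About 25-30% of patients above and 10% below the target range (Protocol 1.2.2). 70 patients on MGL-3196 (SAP 4).

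**1. Conversion.** 1 mg/L = 1,000 ng/mL, so 5000 mg·h/L × 1,000 = 5,000,000 ng·h/mL.

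**2. Ratio to the protocol range.**

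- Top: 5,000,000 / 9,000 = 556.
- Bottom: 5,000,000 / 4,000 = 1,250.
- In the SAP's unit, the protocol range is 4,000 / 1,000 to 9,000 / 1,000 = 4 to 9 mg·h/L.

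**3. Implied concentration.** This assumes a 24-hour AUC, which SAP 3.1 does not state.

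- Average needed to reach the cut-off: 5,000,000 / 24 = 208,333 ng/mL, which is 208,333 / 1,500 = 139 times the Week 2 threshold.
- Averages implied by the protocol range: 4,000 / 24 = 167 to 9,000 / 24 = 375 ng/mL.
- A patient held at exactly 1,500 ng/mL all day: 1,500 × 24 = 36,000 ng·h/mL = 36 mg·h/L, and 36 / 5,000 = 0.72% of the cut-off. This shows scale only. It is not an upper bound, since some patients are expected above 1,500 ng/mL.

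**4. Could individual variation bridge the gap?** The 4,000-9,000 range is a projected mean and target, not a ceiling. As an assumption, take individual AUCs as lognormal with 10% below 4,000 and 25% or 30% above 9,000. Then log-SD = ln(9,000/4,000) / (z_upper + 1.282), with z_upper = 0.674 or 0.524.

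| Share above 9,000 | Median (ng·h/mL) | Log-SD | SDs from median to 5,000,000 | Share above 5,000 ng·h/mL |
|---|---|---|---|---|
| 25% | 6,805 | 0.415 | 15.9 | 77% |
| 30% | 7,112 | 0.449 | 14.6 | 78% |

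The expected number of the 70 active patients above the printed cut-off is effectively zero (below 1e-45). At 5,000 ng·h/mL the AUC condition would divide the arm, with roughly 54 to 55 of 70 above it (70 × 0.771 = 54.0; 70 × 0.784 = 54.9).

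**5. What is left of the rule.** With no AUC above the cut-off, membership depends only on a Week 4 predose level above 1.5 ng/mL. The documents give no trough concentrations, so the share of patients who would qualify cannot be estimated. That figure is one thousandth of the 1,500 ng/mL Week 2 threshold (1,500 / 1.5 = 1,000). A predose level is expected to be lower than a four-hour level, so this ratio does not show an error. It is a reason to confirm the value and unit.

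**The case against.** The strongest reply is that the point rests on one character. If the SAP's source prints µg·h/L, the cut-off is 5,000 ng·h/mL, sits comfortably in the protocol's range, and the main point disappears. The µ symbol does survive in the protocol text (Table 1 and Section 1.2.1), but the SAP text contains no other µ to compare. This reservation stands, and the source PDF should be checked first.

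Second, literal application is unlikely. A programmer with projected AUCs on the protocol's scale would compare them with 5000 and get a usable split, an empty AUC condition would show in the first table, and the stand-alone programming specifications (SAP 5) may carry the right unit. That is plausible, but those specifications are not in the documents. SAP 1 requires departures from the plan to be reported, so the written rule should match the one that is run. The unitless second mention of 5000 does not settle which unit was meant.

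Third, the stakes are limited. The primary comparison in SAP 3.7.2 and the final-dose analyses do not use the grouping, SAP 3.7.3 calls the LDL-C subgroups descriptive, and the multiples above all restate a single factor of 1,000. All of this is correct. Even so, LDL-C change by exposure is a named secondary parameter, and the grouping also enters a safety analysis.

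Fourth, the dose qualifier and the sampling lists are lesser matters. They are, and would not justify a comment alone.

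**Conclusion.** The concern holds. As printed, the AUC cut-off is 5,000,000 ng·h/mL, 556 to 1,250 times the range the protocol projects and targets, and no other text in either document corrects it. Applied literally, the AUC condition is empty. The high-exposure group as a whole need not be, because the predose condition remains. The conversion and ratios are exact. That nobody is selected is an inference, safe at a gap of more than 550-fold even though a quarter or more of patients may exceed the target range.

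The conclusion assumes that the SAP really prints mg and that both documents refer to the same AUC. The uncertainty over the printed character keeps confidence at medium. No error is claimed for the 1.5 ng/mL figure. This concerns an analysis grouping, not the dosing rule, and it should be corrected although the primary result does not depend on it.

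**What to change.** Check the source SAP for the printed unit. Then, before unblinding:

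1. State both AUC mentions in SAP 3.1 in ng·h/mL, or justify mg·h/L. The value compatible with the protocol's scale is 5,000 ng·h/mL. Make the programming specifications agree.
2. Say whether the 60 mg qualifier refers to the dose at the Week 4 predose sample or the dose after Week 4.
3. Confirm the value and unit of the 1.5 ng/mL predose cut-off, with LDL-C results masked.
4. Reconcile the PK sampling lists: the protocol synopsis and SAP 3.9 omit the Week 4 sample that Protocol 8 and SAP 2.3.2 include.

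The cost is one unit correction and one clarifying sentence in SAP 3.1, confirmation of the predose figure, and aligned visit lists. No new data are required.
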